As the Sponsor, Posit Science will serve strictly as a coordinating and data monitoring and management site. The Posit Science study team will manage this study using standard and established methods. Site Study personnel will be invited to complete virtual training sessions conducted by the Posit Science study team and/or the PI will visit the Study Site to engage in a hands-on orientation of the digital application and clinician's portal.

Enrollment and assessments will be performed by authorized site study personnel remotely and/or at the study site, the University of Minnesota. Participants will perform the intervention activities remotely in their place of residence or in-person. This project will employ established Sponsor- and Site-procedures for compliance, treatment delivery and communication to ensure standardization of all study procedures.

The emphasis of the benefit will be on advancing science to assist others with ASD. Compensation will be described in appropriate terms that are not overemphasized relative to the remainder of the text. No indication of "free medical treatment" will be communicated. All materials used for advertising or recruitment will have received IRB approval prior to implementation. The site study personnel will manage these efforts and contact individuals that express interest. The aim of this discussion is to describe the study, answer any questions, and if the potential participant agrees, conduct a preliminary screening. Site study personnel will conduct an interview with a screening questionnaire, over the phone or in person, in which potential participants will be asked about the presence of inclusion and exclusion criteria. If the participant appears eligible, they and their parents/legal guardians, when appropriate, will be invited to a consent discussion.

All study team members are required to follow Good Clinical Practices and institutional best practices in the identification and recruitment of research participants. Volunteer selection will be equitable: all participants meeting Inclusion/Exclusion criteria will be offered the opportunity to participate in this study regardless of gender, race and/or ethnic origin. Basic demographic data will be collected from participants screened for participation but not

meeting study eligibility requirements to ensure that the opportunity to participate in this research study has been extended to all potential participants in an equitable manner.

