- *Extra Time:* Under special circumstances, PEERS session(s) may be paused for 1 or more weeks. This may occur if the PEERS Clinician is unable to conduct the session and no alternate PEERS Clinician is available to conduct the session. In such cases, the intervention will be extended by the number of weeks it has been placed on hold. Participants will resume the PEERS sessions such that all 16 sessions intended for the intervention are delivered to participants.
- *Cessation of Program Use While Continuing Participation in the Study:* In some cases, a participant may wish to stop or minimize use of the program, while remaining in the study. Potential reasons for this decision might include changes in school or work circumstances, changes in residence, health issues, family/personal issues, or a lack of interest in program activities. While the participant will be encouraged to meet their weekly goals, in such cases, after discussion with the site study coordinator, the participant will be permitted to cease using the program and undergo the mid-intervention assessment (V3) or post-intervention assessment (*End of Study*, V4) visit, given they have met the minimum number of sessions required to complete this assessment.
- *Emergency:* All participants will be told how to contact the appropriate site study personnel in the case of an emergency.

Several of these options in aggregate are likely to lead to variation within a group and between groups with regard to the total number of sessions completed, and may cause an imbalance between the number of sessions completed within and between groups. Although this is not ideal, we believe that this is the correct approach given that such flexibility will allow more participants to join the study (compared to no program use flexibility), and reduce attrition. In addition, this approach has the value of more closely mimicking real-world use of the program, increasing the prospective validity of the study. We will continuously monitor the distribution of completed sessions and will consider modifications to the protocol (see *Modifications to the Protocol*) if it appears that this flexibility may be associated with meaningful differences. The data analysis plan is generally robust to variations in the number of sessions completed (see *Data Analysis*).

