### Withdrawal from the Protocol

Study participants may withdraw from the study at any time, for any reason, or for no stated reason. We anticipate that a common reason for study withdrawal will be the time required to complete the intervention. For participants seeking to withdraw for that reason, we will offer the alternative of discontinuing the intervention and scheduling and completing the post-intervention assessment (*End of Study, V4*) visit, given they have met the minimum sessions required to complete the assessment visits. The data analysis plan is structured so that their data will be valuable even if they do not complete the intended number of sessions. Participants who still wish to withdraw following that option will withdraw. Other than time required to use the program, we do not anticipate any common reasons for withdrawal that we will plan for in advance.

In rare cases, a Principle Investigator may decide to prematurely discontinue a participant's involvement in the study for any of the following reasons:

- a) Safety,
- b) Participant non-compliance,
- c) A change in circumstance that would prevent completion of protocol-required assessments,
- d) Participant relocation to an area that, due to great distance, would prohibit a participant from receiving follow-up at the study site,
- e) Participant displays inappropriate behavior toward study staff members or other participants,
- f) Participant is hospitalized for psychiatric reasons;
- g) Loss of funding, or;
- h) A clinical determination, by the Principal Investigator, that continuation in the study is not in the participant's best interests.

Across all reasons for withdrawal, we will ensure an orderly end to the participant's involvement in the study by arranging for the site study coordinator or PEERS clinician to recover the digital device (if it has been issued to the participant), conducting an informational interview with the participant to understand the reasons for study withdrawal and identify any issues with study conduct or adverse events that are relevant, and arrange study compensation for sessions that the participant completed.

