With 48 participants fully evaluated, we will not have enough power to detect a treatment augmentation effect ascribable to CICADAS. However, data from this pilot trial will be used to power a pivotal RCT in Phase II, as they will allow to explore whether:

- a) the concurrent delivery of CICADAS and PEERS for 16 weeks (B1-B2) induces greater improvements sensory processing, cognition, symptom reduction, social skills and behaviors, as well as quality of life, compared to CICADAS only (A1-A2) or PEERS + Active Control (C1-C2) – *preliminary efficacy of CICADAS as a treatment enhancer for PEERS*;
- b) The concurrent delivery of CICADAS and PEERS for 16 weeks (B1-B2) induces greater improvements sensory processing, cognition, symptom reduction, social skills and behaviors, as well as quality of life, compared to the sequential delivery of CICADAS and PEERS (A1-A3) – *preliminary testing of CICADAS as enhancer vs primer*;
- c) improvements sensory processing, cognition, symptom reduction, social skills and behaviors, and quality of life induced by the concurrent delivery of CICADAS and PEERS (B1-B2) are sustained after 16 weeks of no contact (B2-B3) – *durability of augmentation effects*.

To verify these experimental hypotheses, we will conduct the analysis based on the pre-intervention (baseline) and post-intervention data. The criterion for statistical significance is  $p < 0.05$ . Results with  $p < 0.1$  will be described as trends.

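### The withdrawal section lets relocation end study involvement and provides no outcome visit afterwards, although assessments can be remote; removal for behaviour may also be informative, but any resulting bias is possible rather than shown

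*Protocol*

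**What the plan says.** The Protocol's Withdrawal from the Protocol section states: "In rare cases, a Principle Investigator may decide to prematurely discontinue a participant's involvement in the study for any of the following reasons". Item (d) is "Participant relocation to an area that, due to great distance, would prohibit a participant from receiving follow-up at the study site" and item (e) is "Participant displays inappropriate behavior toward study staff members or other participants". What ends is involvement in the study, not only the intervention.

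The section then adds: "Across all reasons for withdrawal, we will ensure an orderly end to the participant's involvement in the study". The steps named are recovering the device, an interview about the reasons for leaving, and payment. No outcome visit is listed. For participants who want to leave because of the time required, the same section says "we will offer the alternative of discontinuing the intervention and scheduling and completing the post-intervention assessment", subject to a minimum number of sessions.

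Other parts of the plan point the other way:

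- Protocol, Recruitment: "Enrollment and assessments will be performed by authorized site study personnel remotely and/or at the study site". Study Procedures gives V1 and V4 as remote or in person, and PEERS groups may also meet remotely.
- Protocol, Description of Protocol Devices, on stopping program use while staying in the study: possible reasons include "changes in residence, health issues, family/personal issues, or a lack of interest in program activities". Such participants may attend V3 or V4 if they met the minimum sessions.
- SAP, Primary Outcome - Feasibility: efforts will be made to assess all who completed the minimum activities. These are one hour of app use and, in Arms B and C, one PEERS session as well.

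**The concern.** There are two separate issues.

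The first is avoidable loss. A participant who moves away may be assessable by video, yet item (d) allows involvement to end because the site itself is out of reach. Item (c) already covers changes in circumstance that prevent required assessments. What (d) adds is therefore mainly people who could still be assessed.

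The second is informative loss. Item (e) removes people for social conduct, while social skills and behaviours are secondary outcomes (SRS-2 and SSIS-RS among them). The SAP relies on maximum likelihood, which assumes data are missing at random, and it describes no sensitivity analysis. If such removals were more frequent in one arm, a between-arm contrast could be distorted. The SAP intends to use these data to power the Phase II trial, so a distortion could carry forward.

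**Working it through.** **The plan's own figure.** The Protocol recruits 56 to obtain 48 completers at 15% non-completion. 48/0.85 = 56.5, which rounds up to 57; 48 × 1.15 = 55.2, which rounds up to 56. The stated 56 is reproduced to within one participant. The allowance is 56 − 48 = 8 losses for all reasons. No number is given for losses under (d) or (e). One or two would be 1/8 = 12.5% or 2/8 = 25% of that allowance.

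**Relocation: the passages side by side.**

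| Place | Effect of a move |
|---|---|
| Withdrawal, item (d) | Study involvement may end because the site cannot be reached |
| Withdrawal, exit steps | No outcome visit |
| Recruitment; Study Procedures | Assessment may be remote |
| Description of Protocol Devices | Program may stop; V3 or V4 still attended, given minimum sessions |
| SAP, Primary Outcome - Feasibility | Effort to assess all with minimum activity |

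A site that follows the first two rows loses data that the other three would collect.

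**Behaviour: where opportunity differs by arm** (Protocol, Treatment Arms). Item (e) has two limbs. Conduct toward staff can arise in every arm. Conduct toward other participants needs contact with them, chiefly in PEERS groups: Arms B and C in weeks 1-16, Arm A in weeks 17-32.

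- B1-B2 versus A1-A2: group exposure differs (16 weeks against none).
- B versus C over stage 1: group exposure is the same.
- B1-B2 versus A1-A3: each side has 16 weeks of groups before its endpoint.

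The last line follows the Protocol and the SAP's own comparison (b). One sentence in the SAP's Statistical Plan puts all three arms on no contact in the second period; I take the Protocol's description for Arm A.

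**Size, as an illustration.** Take 16 per arm and a normally distributed outcome (assumed).

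1. Standard error of a two-arm difference: √(2/16) = 0.354 SD.
2. Ceiling for one removal, if that person is the worst of 16: the expected minimum is −1.77 SD, so the mean of the rest rises by 1.77/15 = 0.12 SD.
3. Ceiling for two removals, the two worst (by simulation): 0.22 SD.
4. Milder case: k of 16 removed, each d SD worse than those retained, gives a shift of (k/16) × d. With k = 1 or 2 and d = 0.5 to 1.5, this runs from (1/16) × 0.5 = 0.03 to (2/16) × 1.5 = 0.19 SD.
5. With baseline kept in the mixed model and an assumed baseline-to-follow-up correlation r, the ceilings shrink by about 1 − r². For r = 0.5 to 0.8: 0.12 × 0.75 = 0.09 down to 0.12 × 0.36 = 0.04 SD for one, and 0.22 × 0.75 = 0.17 down to 0.22 × 0.36 = 0.08 SD for two.
6. If the conduct correlates only 0.5 with the outcome (assumed), these halve to about 0.02-0.05 SD and 0.04-0.08 SD.

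A contrast is biased only to the extent that removals differ between its arms.

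**The case against.** The strongest reply is that little here is automatic. The investigator may discontinue, only in rare cases, and (d) applies only where distance would prohibit follow-up. The residence provision concerns a participant who chooses to stop the program, whereas (d) is an investigator's option, so they are not strictly opposite rules for one event. The Protocol also invites some participants with loaned devices who cannot be reached to return for a follow-up visit. Principal Investigators are to remain blinded. The efficacy outcomes are secondary and, by the SAP's own statement, underpowered. People removed for conduct toward staff cannot simply be sent back to staff-run visits.

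Most of this stands, and it limits the claim. It does not remove the mismatch between (d) and remote assessment, or the absence of any outcome visit from the exit steps. Blinding helps only in part: under Study Personnel, the sponsor's Principal Investigator monitors the PEERS Zoom chat, and presence in a first-period group shows that a participant is not in Arm A.

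A reader might infer that both reasons remove people in relation to the outcome and unequally by arm, so that the comparisons tilt toward the PEERS arms. The documents do not support that. Relocation has no shown link to outcome or arm. Arm A also meets staff, so (e) can arise there. B and C have equal group exposure. In the concurrent-versus-sequential comparison Arm A has its own PEERS groups, so no direction follows.

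**Conclusion.** The inconsistency over relocation is established by the text: followed as written, the withdrawal section can lose outcome data that the rest of the plan would collect. Nothing shows that this loss would be biased.

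For behaviour, the removal is plausibly informative, and maximum likelihood would not fully correct it. The SAP's within-group effect sizes from mean change scores also need observed follow-up. Any between-arm bias is possible rather than shown, and it is confined mainly to B1-B2 versus A1-A2 in stage 1.

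The figures of 0.12 and 0.22 SD are worst-case ceilings on a raw completer mean, about 0.12/0.354 = 0.34 and 0.22/0.354 = 0.62 of a standard error. They assume one or two removals, normality, and that the worst scorers are the ones removed. With baseline in the model they fall below half a standard error (0.17/0.354 = 0.48). Only secondary outcomes are exposed: a participant removed after starting can still count as a non-completer in the primary feasibility rates.

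**What to change.** - Reconcile withdrawal item (d) with the remote-assessment provisions under Recruitment and Study Procedures, with the residence provision under Description of Protocol Devices, and with the SAP's statement on assessing all who met the minimum activities.
- Separate, in the text, discontinuing an intervention or group from discontinuing outcome assessment.
- State that participants discontinued under (d) or (e) who have not withdrawn consent are still invited to V3 and V4. These would be done remotely, or by parent-report and self-report measures where staff protection requires it. Add this to the exit steps.
- Report discontinuations by reason, arm and period.

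Who may be removed from an intervention or group, and when, stays with the investigator; no rule on that is proposed here.

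The cost is Protocol and SAP wording, some extra coordinator contact, and a few remote assessments. The sample size does not change.

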### **Modifications to the Protocol**

Any significant changes to the protocol, including changes to inclusion/exclusion criteria, changes to assessments, changes to recommended intervention and/or program use, changes that could potentially increase risk to study participants, and additions or removals of key personnel and/or recruitment sites will have to be approved by the PIs. Changes requiring approval by the Institutional Review Board will be submitted for review in the form of a protocol amendment or revision prior to implementation.

### **Protocol Deviations**

Protocol deviations will be noted and recorded by study staff (PI, Study Coordinator, Psychometrician, or PEERS Clinician) if they detect the deviation. All protocol deviations will be reviewed by the Sponsor PI ([name]) on a monthly basis and must be signed off by the Site PI; any such deviations suggesting systematic problems with the protocol procedures as implemented by the site will be reviewed and corrective action determined and implemented by the site.

### **Reporting of Serious Adverse Effects & Unanticipated Device Effects**

The CICADAS protocol has minimal risk, and previous studies of similar approaches in psychiatric populations have not reported significant adverse events arising from intervention

and program use. Additionally, computerized treatment studies using Posit Science software in healthy aging, schizophrenia, and TBI have never reported adverse events attributable to study activities. Nonetheless, to follow best practices for treatment trials in medical indications, we will employ a central Medical Research Monitor to review all unanticipated problems involving risk to participants, serious adverse events, and any participant deaths associated with the protocol, and provide an unbiased written report of the event within ten calendar days. The Medical Research Monitor will comment on the outcomes of the adverse event and relationship of the event to the protocol or test article. The Medical Research Monitor will also indicate whether they concur with the details of the report provided by the study staff member. Reports for events determined by designated study personnel, i.e. Medical Research Monitor, to be possibly or definitely related to participation, and reports of events resulting in death will be promptly forwarded to Western IRB. Further, serious adverse events attributable to study activities and/or the intervention and/or program use, will be documented and reported immediately to the Western IRB. An event that is serious must be recorded on the case record and requires expeditious handling to comply with regulatory requirements. In the event that a patient becomes ill or injured as a direct result of participation in the project, necessary medical care will be made available.

The site study coordinator and PEERS clinician will ask about any deterioration in symptoms during each contact with participants, and will be alert to any volunteered episodes of suicidality. All events of this nature will be documented on a standardized form and will be classified by the PI to their degree of seriousness and their relationship to the study protocol. Participants will be referred to appropriate clinical care should there be any concerns for safety or increasing symptoms. If deemed clinically necessary, the PI may elect to remove participants from the study if they find that it is no longer in the participant's best interests to continue participation in the study.

Finally, we will also conservatively follow guidelines for medical devices (i.e., computerized assessments) in the reporting of adverse events in this trial, which defines unanticipated adverse device effects (UADEs) in The Code of Federal Regulations in 21 CFR 812.3(s) as any serious adverse effect on health or safety associated with, a device.

### **Continuing Review and Final Report**

In accordance with NIH SBIR guidelines, a continuing review report(s) as well as a Final report will be submitted via eRA Commons.

The knowledge of any pending compliance inspection/visit by the FDA, Department of Health and Human Services Office for Human Research Protection, or other Government agency concerning clinical investigation or research, the issuance of Inspection Reports, FDA Form 483, warning letters, or actions taken by any Regulatory Agencies, including legal or medical

actions, and any instances of serious or continuing noncompliance with the regulations or requirements will also be reported.

## **Surveys, Questionnaires and Other Data Collection Instruments**

\*Complete paper versions are available upon request.

### **Confirmation of ASD**

*The Autism Diagnostic Interview-Revised (ADI-R)*

<https://www.wpspublish.com/adi-r-autism-d-revised>

*Autism Diagnostic Observation Schedule, 2nd Edition (ADOS-2)*

<https://www.wpspublish.com/ados-2-autism-diagnostic-observation-schedule-second-edition>

### **Cognitive Function**

*Wechsler Abbreviated Scale of Intelligence (WASI-II)*

<https://www.pearsonassessments.com/store/usassessments/en/Store/Professional-Assessments/Cognition-%26-Neuro/Wechsler-Abbreviated-Scale-of-Intelligence-%7C-Second-Edition/p/100000593.html>

*Behavior Rating Inventory of Executive Function, Second Edition (BRIEF-2)*

<https://www.parinc.com/Products/Pkey/24>

*Mind Bender*

<https://www.brainhq.com/why-brainhq/about-the-brainhq-exercises/intelligence/mind-bender/>

*PsyToolkit's Eriksen Flanker and Wisconsin Card Sorting Tasks*

<https://us.psychtoolkit.org/experiment-library/flanker.html>

<https://us.psychtoolkit.org/experiment-library/wcst.html>

### **ASD-related Behaviors**

*Repetitive Behavior Scale - Revised (RBS-R)*

*Social Responsiveness Scale, Second Edition (SRS-2)*

<https://www.wpspublish.com/srs-2-social-responsiveness-scale-second-edition>

*Achenbach System of Empirically Based Assessment (ASEBA) - Age Dependent: Child Behavior Checklist (CBCL - parent report), Youth Self Report Form (YSR), Adult Self-Report (ASR), or Adult Behavior Checklist (ABC)*

<https://aseba.org/school-age/>

<https://aseba.org/adults/>

## **Social Cognition**

*Dynamic Affect Recognition Evaluation (DARE)*

*Social Skills Improvement System - Rating Scales (SSIS-RS)*

<https://www.pearsonassessments.com/store/usassessments/en/Store/Professional-Assessments/Behavior/Social-Skills-Improvement-System-SSIS-Rating-Scales/p/100000322.html#:~:text=The%20Social%20Skills%20Improvement%20System,problem%20behaviors%2C%20and%20academic%20competence.>

*Test of Adolescent Social Skills Knowledge (TASSK)*

Laugeson, E. A., Frankel, F., Mogil, C. & Dillon, A. R. Parent-Assisted Social Skills Training to Improve Friendships in Teens with Autism Spectrum Disorders. *J. Autism Dev. Disord.* **39**, 596–606 (2009).

